## **LIST OF ABBREVIATIONS**

AE Adverse Event

CFR Code of Federal Regulations

CRF Case Report Form

IEC Independent Ethics Committee

FDA Food & Drug Administration

GCP Good Clinical Practice

ICF Informed Consent Form

ICH-GCP International Conference on Harmonization – Good Clinical Practice

IEC Institutional Ethics Committee

IRB Institutional Review Board

PI Primary Investigator

PDC Porcine Derma Collagen

QOL Quality of Life

SAE Serious Adverse Event

VAS Visual Analog Scale

## I. Background

#### 1.1 Introduction

In hernia repair, implants of various materials are often chosen as a means of reinforcing the tissue in the region of the herniation, and ensuring a greater likelihood of success, as measured by a lower incidence of recurrence. In primary closure, the recurrence rate has been cited as ranging from 24 to 66% [9,3,12] while the number has been reported as significantly lower when an implant was used for the repair.[11]

The use of implants in hernioplasties has been well documented and for this reason it is often a preferred procedure. One of the more common types of material for the prostheses used in hernioplasties is polypropylene implant, but the use of this material in contaminated fields is controversial. In complex hernias, such as large or small bowel resections, the surgical procedures are often potentially contaminating. Therefore, the use of certain materials such as polypropylene can be hazardous due to bacteria colonizing the mesh.[5] In addition, in the case of a large abdominal wall defect the use of a prosthetic device is mandatory, however it needs to be noted that it is not possible to use polypropylene in direct contact with bowel. [10,6]

When using an acellular dermal matrix derived from porcine in complex hernias, positive surgical results have been shown with no observed recurrences, while wound infections observed after a mean follow-up of 11.1 months showed no significant difference compared to primary closure. [1] Shaikh (2007) has also reported that recurrence rates for porcine acellular dermal matrix are similar to the recurrence rates when using synthetic materials. [13] A case study that used porcine acellular dermal matrix in a contaminated field, although limited in scope, has also shown positive surgical outcomes at one year post-surgery.[7] In an exposed bowel, Chuo, et al (2008) has demonstrated positive outcomes in patients with a variety of surgical situations including exposed bowel, contaminated abdominal wound beds and around stomas. [2] These outcomes certainly seem to support the animal models which have shown that biologic grafts, in comparison to synthetic material, are able to clear a Staphylococcus aureus contamination. [8]

Complex hernias include those that have either been repaired before on multiple occasions, those associated with infections, or those that have resulted in bowel perforations or fistulas. Porcine acellular dermal matrices (ADM) have recently been proposed as a means to offset the disadvantages of polypropylene synthetic implants, for example their inability to integrate into the patient's tissue thus creating a site for bacteria to colonize, and have since been used in humans for hernia repairs. While the polypropylene synthetic implants are permanent, the acellular dermal matrix implants have been shown to incorporate into the host, with the implanted tissue remodeling to resemble the original tissue, both histologically as well as functionally. The product we plan to use is a porcine acellular dermal matrix which will have been processed via the Tutoplast® Tissue Sterilization Process.

Animal models have been used extensively to assess implantable materials generally and implants of various materials for soft-tissue reinforcement in particular, despite significant limitations. 2 A recent systematic review of biologic implants in animal studies concluded that supplemental cross-linking of collagen in tissue-based implants did not adversely affect the strength of the implant or its ability to support long-term ingrowth of native tissue. 11 The limitations of animal models have, however, been clearly exposed recently by the comparison of the same two porcine dermal implants, PermacolTM

(supplemental cross-linked; Covidien, New Haven, CT, USA) and Strattice™ Reconstructive Tissue Matrix (non-supplemental cross-linked; LifeCell Corporation, Bridgewater, NJ, USA), in different animal models, with startlingly differing results. 12.13 Therefore, the extrapolation of results from animal data to the clinical context should be performed with caution. The choice of porcine acellular dermal matrices by the surgeon should be based on the evidence available from clinical studies pertinent to the context in which it is being used (www.ncbi.nlm.hih/gov/pmc/articles/PMC3956623/).

#### 1.2 Rationale

Biologic materials such as Fortiva Porcine Dermis and Strattice Reconstructive Tissue Matrix were developed to provide reinforcement of hernia repair. However, limited high quality prospective data exists on the use of these materials in complex abdominal wall reconstruction, and no comparative data exists. Therefore the objective of this study is to compare the effectiveness of Fortiva Porcine Dermis versus Strattice Reconstructive Tissue Matrix for the underlay reinforcement of complicated ventral hernia repair and assess post-operative complication rates, long term hernia recurrence rates.

#### **II. Study Design**

This is a randomized, prospective, double-blinded study evaluating the efficacy of Fortiva Porcine Dermis versus Strattice Reconstructive Tissue Matrix in 120 patients with large complex abdominal wall ventral hernias undergoing single stage repair. The patient will be blinded to treatment as well as an independent qualified evaluator to confirm evidence of reoccurrence. This post-market study compares two FDA cleared biologic hernia materials. Fortiva™ porcine dermis, processed by RTI Surgical, Inc., a non-cross linked porcine dermis will be compared to Strattice™ Reconstructive Tissue Matrix by LifeCell, a non-cross linked porcine dermis for reinforcement during the single stage open reconstruction of abdominal wall defects. The primary outcome will be hernia recurrence at 1 year. Outcomes will be evaluated at 6 weeks, 3 months, 6 months and 12 months and 24 months.

#### 21 CFR 812

As devices that have been cleared for marketing and being investigated in accordance with its cleared indications and cleared labeling, the Study entitled "A Randomized, Prospective Study Comparing Fortiva vs. Strattice in Patients Undergoing Open Primary Ventral Hernia Repair" is exempt from IDE regulations according to 21 CFR 812.2(c) (2).

A device, other than a transitional device, introduced into commercial distribution on or after May 28, 1976, that FDA has determined to be substantially equivalent to a device in commercial distribution immediately before May 28, 1976, and that is used or investigated in accordance with the indications in the labeling FDA reviewed under subpart E of part 807 in determining substantial equivalence.

## 2.1 Treatments

The study will involve participants who are planning to undergo an elective large, complex abdominal wall hernia repair. The specific definition of this population is described in the Inclusion/Exclusion criteria. Participants must be able to participate in the informed consent process and be willing to adhere to the follow up required for this two (2) year study. The treatment includes hernia repair reinforcement with one of the following two hernia repair meshes:

- Fortiva™ Porcine Dermis
- Strattice™ Reconstructive Tissue Matrix

Fortiva™ Porcine Dermis is an implantable device comprised of non-crosslinked acellular porcine dermis that has been processed via the Tutoplast tissue sterilization process, terminally sterilized and is stored hydrated and ready to use. The implant is designed to be used in soft tissue repair and provides a strong, biocompatible scaffold that incorporates into host tissue.

Strattice™ Reconstructive Tissue Matrix is an acellular reconstructive tissue matrix designed to support tissue regeneration. It is derived from porcine dermis, which undergoes non-damaging proprietary processing that removes cells and significantly reduces the key component believed to play a major role in the xenogeneic rejection response.

## 2.2 Surgical Technique:

The major source of structural integrity and strength of the abdominal wall is provided by the musculofascial layer. The main paired abdominal muscles include the external oblique muscles, internal oblique muscles, transversus abdominis muscles, and rectus abdominis muscles and their respective aponeuroses, which are interdigitated with each other, and provide core strength and protection to the abdominal wall viscera. The integrity of the abdominal wall is essential not only to protect the visceral structures but also to stabilize the trunk and to aid trunk movement and posture.

Complex abdominal wall defects, including incisional abdominal wall hernias, are a challenging surgical problem. Incisional hernias occur in 10 to 23 percent of open abdominal laparotomies, with recurrence rates reported between 18 and 50 percent (deHartog, et al, 2008; Lowe et al. 2000^15, Sailes et al, 2011 .). The Component Separation Technique (CST), a type of rectus abdominis muscle advancement flap, was first used to reconstitute the linea alba, reduce abdominal wall tension, and provide a dynamic abdominal wall in patients with large abdominal wall defects (Ramirez et al. 1990^17). CST allows reconstruction of a large defect without requiring a free distant transposition flap (de Vries et al. 2003). The advantages of CST are that it restores structural support of the abdominal wall, provides stable vascularized soft tissue coverage, and optimizes aesthetic appearance of complex abdominal wall defects and giant midline abdominal wall hernias (Shestak et al. 2000). In this protocol, abdominal wall mobilization will be conducted in an attempt to bring the fascia together. If this is unable to be completed with circumferential undermining, component separation will be performed bilaterally.

Patients will then be randomized 1:1 to one of two treatment assignments:

- Fortiva™ Porcine Dermis retrorectus/underlay
- Strattice™ Reconstructive Tissue Matrix retrorectus/underlay

Procedure: After the abdominal wall mobilization is completed, and the Investigator determines that the primary fascial closure can be obtained, the assigned implant will be prepared according to the manufacturer's instructions and will be immediately available for the surgery.

We will utilize the Rives-Stoppa technique which begins by vertically incising the posterior rectus sheath 0.5-1cm from its medial edge. The posterior rectus sheath is separated from the rectus muscle thereby creating a retromuscular plane. This plane is developed bilaterally until the linea semilunaris preserving the perforators to the rectus muscle. After this is completed, the implant will be implanted in the retrorectus position assuring at least 3-5 cm of overlap of the defect with normal tissue. (If this technique still does not allow for primary closure, the investigator may alternatively perform a posterior component separation (Novitsky et al. or anterior component separation as per the investigators decision).

Please note that the peritoneum will be closed prior to securing the implant with a running #0 Vicryl suture. Then utilizing a parachute technique, full thickness (through fascia and implant) No. 1 PDS suture will be sewn in an interrupted fashion to implant. Please note that two (2) sutures will be placed inferiorly in Cooper's ligament as well as two (2) sutures superiorly in the subcostal area with #1 PDS as appropriately needed to secure the implant as per the investigator. A Central suture will also be placed to ensure appropriate placement between these sutures. The investigator will be sure that the implant is sewn in with moderate tension. The overlying fascia will be closed with simple interrupted No.1 PDS suture in vertical mattress or Figure of 8s fashion (as per the investigator) over the biologic implant. If the fascia is not able to be entirely closed (a bridge of implant exists without overlying fascia), the subject will be withdrawn from the study and will be considered a "screen failure". Data captured up until this point will not be included in the primary analysis. Please note that if the retrorectus space is obliterated, the implant may be placed beneath the peritoneum and again sewn in via a parachute technique with #1 PDS in a simple interrupted fashion incorporating fascia, peritoneum and implant. After the implant has been secured, the fascia is closed in vertical mattress fashion with #1 PDS over the implant.

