## 5.3 Enrollment and Subject Number Identifiers

#### 5.3.1 Enrollment

Upon signing an approved Informed Consent Form subjects will be assigned a unique subject number.

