#### 5.3.2 Randomization

Patients who are consented and enrolled in the study will be randomized to receive either one of the two hernia repair implant interventions. Randomization will be 1:1. Patient numbers were allocated to a study arm based on pre-established randomization tables. Randomization tables were created using ranblock.exe (Menne Biomed Software, Tübingen, Germany). Sealed envelopes were prepared with patient specific numbers and provided to the site. If a patient is withdrawn after they have been assigned a number, the envelope with the corresponding patient number will be considered non-transferable and may not be forwarded to another patient. The subject will be blinded to their treatment arm, but the surgeon will not.

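### The plan does not fix when the envelope is opened, so an unblinded surgeon can judge further release, implant plane and intra-operative withdrawal with the implant known

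*Combined protocol and SAP*

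**What the plan says.** Section 5.3.2 states: "The subject will be blinded to their treatment arm, but the surgeon will not". Section II adds that the patient and an independent evaluator who confirms recurrence are blinded.

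The time of allocation is described in two places.

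- Section 2.2 describes mobilisation and continues: "If this is unable to be completed with circumferential undermining, component separation will be performed bilaterally". After that comes: "Patients will then be randomized 1:1 to one of two treatment assignments". The assigned implant is prepared once mobilisation is complete and the investigator judges that the fascia can be closed.
- Section 5.3.1 reads: "Upon signing an approved Informed Consent Form subjects will be assigned a unique subject number". Section 5.3.2 reads: "Patients who are consented and enrolled in the study will be randomized to receive either one of the two hernia repair implant interventions", and "Sealed envelopes were prepared with patient specific numbers and provided to the site". It does not say when an envelope is opened.

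After the randomisation step, section 2.2 sets out the Rives-Stoppa retrorectus dissection as the technique to be used. If this still does not allow closure, the surgeon may add a posterior "or anterior component separation as per the investigators decision". The plane may also change: "if the retrorectus space is obliterated, the implant may be placed beneath the peritoneum". If the fascia cannot be fully closed, the subject is withdrawn as a screen failure and the data are left out of the primary analysis. Sections 5.2.1 and 6.2.1 add intra-operative withdrawal for a defect under 200 cm2 and for active infection.

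**The concern.** The trial asks whether one implant does better than the other within the same repair. That needs the rest of the operation, and the decision to keep a subject in the trial, to be independent of the implant. Here a surgeon who may know the implant judges whether closure is achievable, which release to add, whether the retrorectus space is usable and whether the subject is withdrawn.

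If those judgements leaned differently by arm, a difference in recurrence, fluid collection, infection or dehiscence would mix implant with technique. Intention-to-treat analysis does not separate the two, and adjusting for choices made after randomisation is not clean. Withdrawal after the arm is known is a second route: it removes randomised subjects from the primary analysis, which sits badly with the intention-to-treat principle in section 3.2.

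**Working it through.** No stated figure decides this point. The sample size of 120 cannot be used to gauge it, because section 3.1 gives no recurrence rates or hazard ratio. The check is therefore of sequence: which decisions can be made with the arm known under each reading.

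| Decision (section) | Opened at the point given in 2.2 | Opened between consent and surgery (open under 5.3.1 and 5.3.2) |
|---|---|---|
| First bilateral component separation (2.2) | Before the arm is known | Can be after |
| Judging that the retrorectus technique does not allow closure (2.2) | After | After |
| Adding a posterior or anterior release (2.2) | After | After |
| Judging the retrorectus space obliterated and changing plane (2.2) | After | After |
| Withdrawal for incomplete closure (2.2, 6.2.1) | After | After |
| Withdrawal for defect size or active infection (5.2.1, 6.2.1) | Order not stated | Can be after |

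Four rows are exposed on either reading. The first is exposed only if the envelope is opened before surgery.

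Section 2.2 has a further tension. The assigned implant is prepared once closure is judged obtainable, yet the later text provides for a release when closure is not obtained. So the judgement on closure is revisited after the implant has been identified.

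Safeguards, taken in turn:

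- The note after 5.3.2 on keeping the investigator blinded before randomisation concerns enrolment bias and ends at randomisation.
- The blinded evaluator in section II protects the assessment of recurrence, not the conduct of the operation.
- Section 6.2.1 requires operative details, graft dimensions, fixation and photographs. This makes a difference in technique visible but does not prevent it, and nothing requires the choices to be fixed before the arm is revealed.
- Section 3.2 plans Fisher's exact test for categorical outcomes, with no comparison of technique by arm.

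**Illustration only.** Suppose the implants are equivalent, one technique carries recurrence risk r and the other r × RR, and the second is used in a fraction u of each arm. Then:

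false difference = (u₂ − u₁) × r × (RR − 1)

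Take r = 18%, the lower end of the 18 to 50% range in 2.2. The values u₁ = 40%, u₂ = 60% and RR are assumptions with no source in the documents; RR = 2.78 takes 18% to 50%.

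| RR | False difference | Rejection rate, 60 per arm |
|---|---|---|
| 1.5 | 0.20 × 0.18 × 0.50 = 1.8 points | 5.6% |
| 2.0 | 0.20 × 0.18 × 1.00 = 3.6 points | 7.3% |
| 2.78 | 0.20 × 0.18 × 1.78 = 6.4 points | 11.4% |

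The rejection rate is for a two-sided 5% two-proportion test by normal approximation. With equal use in both arms, the difference is 0 and the rate 5.0%. For scale, one recurrence in an arm of 60 is 1/60 = 1.7 points.

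**The case against.** The strongest reply is that the sections fit together: number at consent, envelope sealed until surgery, opened where 2.2 says. A number tied to a sealed envelope fixes the assignment but does not disclose it. That is right. A reader might infer from 5.3.1 and 5.3.2 that the surgeon knows the arm from consent; the documents do not say so. What they lack is an opening time.

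A reader might also infer that every important operative choice follows allocation. Section 2.2 does not support this. It places the first bilateral component separation before randomisation, and it prescribes retrorectus dissection. The later release and the change of plane have stated triggers. The discretion lies in judging those triggers and choosing the release type. That is narrower, but it stays with an unblinded surgeon.

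A third temptation is to attach a size. For example, one could assume that a release cuts recurrence by 33 to 50% and that its use differs by 10 to 20 points between arms. At base rates of 18 to 50% this gives 0.10 × 0.18 × 0.33 = 0.6 points up to 0.20 × 0.50 × 0.50 = 5.0 points. The reduction and the imbalance have no source in the documents. The model also fits poorly: the later release is for patients who could not otherwise be closed, and unclosed patients are withdrawn, so the same patient kept in the trial without the release is largely not the comparison that arises.

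Finally, both products are non-cross-linked porcine dermis with the same assigned position, and no reason for arm-specific technique is given. A surgeon handling the implant will often be unblinded. This limits how likely the bias is. It does not explain why the arm should be known before decisions that could be settled first.

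**Conclusion.** The point holds as a gap in timing. The surgeon is unblinded, the opening time is not consistently stated, and on either reading the further release, the implant plane and withdrawal for incomplete closure can be decided with the arm known. The first component-separation step is exposed only if the envelope is opened before surgery.

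The documents do not show that technique or withdrawal will differ by arm, and they give no recurrence rates by technique. The size of any bias therefore cannot be derived, and the illustrative figures show only the direction and form of the problem. That technique affects outcome is itself an assumption, supported in the documents only by the statement in 2.2 that component separation lowers tension and restores support. The change should be made because it is cheap and removes most of the exposure; this is not a finding that the trial is biased.

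**What to change.** Reconcile 2.2, 5.3.1 and 5.3.2 by stating one opening time in both 2.2 and 5.3.2. The sealed envelope is opened in the operating room after mobilisation, retrorectus dissection and any component separation are finished, and after intra-operative eligibility (defect area, absence of infection, expected closure) is confirmed.

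- Before opening, enter the release type and intended implant plane on the case report form with the time.
- Record any later change of release or plane, and any later withdrawal, with its reason.
- Add to 3.2 a table of release type, implant plane and intra-operative withdrawals by arm.

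The subject number can still be given at consent, provided the envelope stays sealed. No surgical technique or clinical rule is changed.

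The cost is protocol wording, one time-stamped entry, both products available in the room and slightly later implant preparation. Some exposure remains: suture and closure details necessarily follow disclosure, and so does a closure that was expected to succeed but fails.

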#### 3.2 Statistical Plan

Given the 1:1 randomized nature of the clinical trial and to preserve the inherent characteristics of the randomization, analysis by intention-to-treat (ITT) is chosen. This type of analysis compares the study groups in terms of the treatment to which they were randomly allocated, irrespective of the treatment they actually received or other trial outcomes. Regardless of protocol deviations and participant compliance or withdrawal, analysis is performed according to the assigned treatment group. This type of analysis will also help to demonstrate if there is superiority of one mesh over the other.

If there is no superiority of one mesh over the other, analysis will be performed using the same outcomes to assess if there is equivalence between both meshes. This will demonstrate that there is no clinically significant difference between the two treatment arms.

For statistical analysis, these outcomes can be classified into two measurement scales- continuous and categorical. For continuous outcome, mean and standard deviation, median and range for each group will be calculated. ANOVA will be used to compare the difference in the means among the two groups when data are reasonably normally distributed. Otherwise, non-parametric ANOVA will be used. For categorical data, proportion will be obtained for each outcome, along with 95% CI derived from exact method. Difference in the proportions among the four groups will be compared using Fisher's exact test.

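### Section 2.2 removes from the primary analysis a randomised patient whose assigned implant is already sewn in, which contradicts the intention-to-treat rule in 3.2 and 3.3

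*Combined protocol and SAP*

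**What the plan says.** Section 2.2 (Surgical Technique) sets out the operation in order. The abdominal wall is mobilised, and "Patients will then be randomized 1:1 to one of two treatment assignments". The text goes on: "After the abdominal wall mobilization is completed, and the Investigator determines that the primary fascial closure can be obtained, the assigned implant will be prepared". The implant is then sewn in and the overlying fascia is closed on top of it. If closure is incomplete, so that "a bridge of implant exists without overlying fascia", then "the subject will be withdrawn from the study and will be considered a" screen failure. The consequence for the analysis follows at once: "Data captured up until this point will not be included in the primary analysis".

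Section 3.2 (Statistical Plan) chooses ITT. Groups are compared by allocation, "irrespective of the treatment they actually received or other trial outcomes", and "Regardless of protocol deviations and participant compliance or withdrawal, analysis is performed according to the assigned treatment group". Section 3.3 (Study Population) repeats this.

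On blinding, section 5.3.2 (Randomization) says: "The subject will be blinded to their treatment arm, but the surgeon will not".

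Section 6.2.1, item 5, also withdraws as a screen failure a patient whose abdomen cannot be closed primarily. It does not mention the analysis.

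**The concern.** For a randomised patient left with a bridged repair, the plan gives two answers to whether that patient belongs in the primary analysis. Section 2.2 says no; sections 3.2 and 3.3 say yes. Nothing states which prevails. The comparison of recurrence at or before 1 year depends on the answer, and so does the equivalence assessment that section 3.2 plans on the same outcomes if superiority is not shown.

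The exclusion also comes late. It follows allocation and implantation, and it turns on a judgement by someone who knows which product is in place. Randomisation does not protect against selection at that stage. If bridging, or the decision to call a repair bridged, differs by arm, the patients left in the two arms are no longer comparable.

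**Working it through.** The point is one of consistency, so the main check sets the rules side by side. The planned total of 120 cannot be reproduced, because section 3.1 gives no recurrence rates, hazard ratio or sidedness. Nothing below depends on reproducing it.

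**1. Has the patient been randomised when the exclusion applies?** Yes. Section 2.2 mentions randomisation before the assigned implant is prepared. Section 5.3.2 randomises patients who have consented and enrolled. On either reading randomisation precedes closure. A bridge of implant also presupposes that the implant is in place, so the allocation has been revealed.

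**2. Do the two rules cover the same patient?**

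| | Section 2.2 | Sections 3.2 and 3.3 |
|---|---|---|
| Patient | Randomised, implant sewn in, fascia not fully closed | Any randomised patient |
| Effect of withdrawal | Leaves the study as a screen failure | None on the analysis arm |
| Primary analysis | Excluded | Included as assigned |

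They do, and they conflict. No section defines a modified ITT set or an exception.

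**3. Is the exclusion shielded from knowledge of the arm?** No. The surgeon performs the closure and is unblinded (5.3.2).

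**4. Would the outcome still be collected?** Probably not. Section 2.2 withdraws the patient from the study, and the 12-month examination for recurrence is a study visit (6.7). Section 5.3.3 does not state what outcome follow-up continues after withdrawal by the investigator. Its bar on further study procedures is written for a participant who asks to leave.

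**5. Scale.** Section 3.1 plans 60 patients per arm. The number of bridged repairs, k, is not given, so these values are assumptions.

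- Share of one arm's recurrence rate that rests on the excluded patients = k/60.
- k = 1: 1/60 = 1.7 points. k = 3: 3/60 = 5.0 points. k = 6: 6/60 = 10.0 points.

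These are shares, not expected biases. The shift in one arm's rate from leaving the patients out is f × (r_bridged − r_closed), with f = k/60. If bridged repairs recur 10 to 50 points more often than closed ones (an assumption), then:

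- k = 3: 0.05 × 10 = 0.5 to 0.05 × 50 = 2.5 points.
- k = 6: 0.10 × 10 = 1.0 to 0.10 × 50 = 5.0 points.

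The bias in the between-arm difference is the difference of this product between arms. It is zero if the product is equal in both and can take either sign otherwise.

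**The case against.** The strongest reply is that section 2.2 is a specific, prespecified rule that names the primary analysis, while 3.2 and 3.3 are general. On this view the trial is meant to study closed, reinforced repairs, and the screen failure label is used consistently for intra-operative ineligibility, including a defect found to be too small (5.2.1) and active infection (6.2.1, item 4). All that is missing is a named analysis set. The closability check also makes such cases rare.

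Part of this stands. Cases should be few, and naming a modified ITT set would remove the contradiction in wording. But 3.2 and 3.3 cover withdrawal expressly and allow no exception, and a label does not undo randomisation. A named set would also keep a post-randomisation exclusion decided by an unblinded surgeon, so it is the weaker remedy.

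A reader might infer that the ITT result for these patients could only be bounded. That goes too far: follow-up after investigator withdrawal is left unstated, and censoring or imputation would be possible, though each rests on assumptions. A reader might also set section 5.3.3, which keeps data already collected when consent is withdrawn, against section 2.2. The two are not comparable: 5.3.3 concerns data remaining in the study, while 2.2 concerns one analysis.

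**Conclusion.** The contradiction is real and concerns the primary analysis set, so it must be resolved before analysis. The case rests on two facts in the documents: two incompatible rules for the same patient, and an exclusion after implantation decided by a surgeon who knows the arm.

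The case does not rest on a demonstrated numerical effect. A reader might infer a material bias, or one that favours a particular product. The documents support neither. They give no bridging rate and no recurrence rate for bridged repairs, and an equal effect in both arms would leave the difference unbiased. The 1.7 points per excluded patient is a scale marker. Section 3.1 allows 15 to 20% dropout (9 to 12 of 60 per arm) but does not say whether that covers these patients.

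Section 6.2.1, item 5, might be read as a second breach. It can equally be read as a check before implantation, and it is silent on the analysis. It needs aligning and is not itself the conflict.

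**What to change.** Reconcile section 2.2 and section 6.2.1, item 5, with sections 3.2 and 3.3. For any patient whose allocation has been revealed:

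- delete the screen failure label and the exclusion from the primary analysis;
- keep the patient in the ITT set, in the assigned arm, with the scheduled outcome visits including 12 months;
- report fully closed repairs only as a sensitivity analysis;
- list bridged cases by arm.

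A secondary clarification would help. Section 5.3.2 should say when the envelope is opened relative to the intra-operative eligibility checks. This would be a new statement: section 2.2 mentions randomisation before the closability judgement and does not fix the moment of opening. It must also be reconciled with the assignment of subject numbers at consent (5.3.1), the allocation of numbers to arms by table, and the non-transferable envelope (both 5.3.2). A patient removed before opening still uses up an allocation, so such removals should be counted separately.

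The cost is amendment wording in 2.2, 5.3.2 and 6.2.1 and follow-up of a few more patients. The downside is that a few bridged repairs enter the ITT set; the sensitivity analysis shows how far they matter. No change to surgical technique is proposed.
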